12.8. Appendix 8: Values of Potential Clinical Importance

12.8.1. Laboratory Values

Haematology				
Laboratory Parameter	Units	Category	Clinical Concern Range	
			Low Flag (< x)	High Flag (>x)
Haematocrit	Ratio of 1	Male	0.39	0.54
		Δ from BL	↓0.075	>10%
Haemoglobin	g/L	Male	124	180
		Δ from BL	↓25	>10%
Lymphocytes	x10 ⁹ / L		0.75	4.5
Neutrophil Count	x10 ⁹ / L		1.5	8.0
Platelet Count	x10 ⁹ / L		100	550
White Blood Cell Count (WBC)	x10 ⁹ / L		2.5	15

Clinical Chemistry				
Laboratory Parameter	Units	Category	Clinical Concern Range	
			Low Flag (< x)	High Flag (>x)
Albumin	g/L		30	
Calcium	mmol/L		2.00	2.75
Creatinine	μmol/L			1.3 X ULN
		Δ from BL		↑ 44.2
Glucose	mmol/L		3	9
Potassium	mmol/L		3	5.5
Sodium	mmol/L		130	150
Total CO ₂	mmol/L		18	32
Creatinine kinase	mg/dL			>1.6 X ULN
C-reactive protein	mg/L			≥3.0

Liver Function				
Test Analyte	Units	Category	Clinical Concern Range	
ALT/SGPT	IU/L	High	≥2xULN	
AST/SGOT	IU/L	High	≥2xULN	
AlkPhos	IU/L	High	≥2xULN	
T Bilirubin	μmol/L	High	≥1.5xULN	
T. Bilirubin + ALT	μmol/L IU/L	High	ALT≥3xULN AND bilirubin≥ 1.5xULN	

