1.3.2. Study periods 1, 2, 3 and Early Withdrawal

When the following assessments are scheduled to be performed at the same time-point, the order will be as follows:

ECG > vital signs > PK and PD sampling > PainCart

Procedure	Study periods 1, 2, 3 (Days)								Early Withdrawal	Notes
	-2	-1	1	2	7	8	15	25		
Out-patient visit					X*	X	X		X	Optional in-clinic stay for participants at the discretion of investigator. *Day 7 is optional for those participants not receiving UVB.
Admission in clinical unit	X**									Optional in-clinic stay for participants at the discretion of investigator ** If subjects are not UVB-MITT participants, optional admission will be on Day-1 with Day-2 assessments completed on Day-1.
Discharge from clinical unit				X						Except if, the participant needs to remain in the Unit longer for medical reasons.
Phone Call							X			AE collection - may be out-patient visit at discretion of Investigator for additional checks
Brief Physical Examination			X	X		X	X		X	
Haematology, clinical chemistry (include liver chemistries) and urinalysis		X	X	X		X	X		X	Troponin T to be assessed on Day -1, 8, 15 (and EW if needed). C3/C4 on Day -1 only
UrDrug, BrAlc		X			X*		X			*for volunteers who do not receive UVB application, the Day 7 Assessments may be performed on Day 8 prior to PainCart
SARS-CoV-2 PCR test or rapid antigen test	X**								X	

Procedure	Study periods 1, 2, 3 (Days)								Early Withdrawal	Notes
	-2	-1	1	2	7	8	15	25		
12-lead ECG		T	X			X	X		X	Day 1: pre-dose (T), 0.5hr, 1hr post start of infusion. On other days a single measure taken prior to 1 st PainCart assessment. T = Triplicate X = Single
Vital signs (including temperature)	X**	X	X	X	X-t	X	X		X	Day 1: pre-dose, 0.5hr, 1hr, 2hr post start of infusion. X-t: temperature assessment on Day 7 for UVB-MITT population only On other days a single measure taken prior to 1 st PainCart assessment.
Randomization			X							Study period 1 only
Drug/placebo IV infusion			X							Continuous infusion over 1 hour

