	
pressure, heart rate) correlate. The heavier heart weights were not dose-related and generally did not show a consistent pattern of increased absolute weights, relative to body weight or brain weight. Refer to IB [GlaxoSmithKline Document Number RPS-CLIN-004032]
 
] for further details.
 
In the 26-week study, a thorough evaluation to investigate the potential for cardiotoxicity which included ECG, echocardiogram, telemetry (blood pressure, heart rate), serum cardiac troponin I, NT-proBNP, heart weight and histopathology, did not identify any treatment-related effects on the heart following doses up to 100 mg/kg/week SC.
 
GSK3858279 did not bind to human heart in the tissue cross-reactivity studies and there is no known pharmacological mechanism following administration of an anti-CCL17 which would lead to an increase in heart weight. Therefore, the potential effect on heart weights noted in the 13-week study in monkey was not reproducible following 26 weeks of chronic dosing in monkey and is not considered to be clinically significant.
 
Clinical
 
During Part A of the FiH study (207804) in healthy participants, none of the abnormal findings in the ECG parameters were judged to be clinically significant.
	
Participant monitoring: Investigations during screening include ECG, echocardiogram and troponin T and NT-proBNP. TroponinT and NT-proBNP will be monitored after dosing.

Bleeding Risk	CCR4, the receptor for CCL17 is expressed on platelets and both CCL17 and CCL22 activate platelets in vitro. A potential risk of impaired platelet activation and blood clotting exists with CCL17	Participant exclusion and non-permitted medication

Potential Risk of Clinical Significance	Summary of Data/Rationale for Risk	Mitigation Strategy

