28. Major surgery (as per investigator's judgement) within 3 months prior to dosing.

Prior/Concurrent Clinical Study Experience

29. Participant has made a blood or plasma donation or has had a comparable blood loss (>450mL) within the last 3 months prior to the Screening Visit. Blood donation during the study is not permitted.
30. Exposure to more than 4 new chemical entities within 12 months prior to the first dosing day.
31. Current enrolment or past participation in any other clinical study involving an investigational study intervention within the last 3 months, 5-half-lives or twice the duration of the biological product before dosing in this current study.

Diagnostic assessments

32. Presence of Hepatitis B surface antigen (HBsAg) at screening or within 3 months prior to first dose of study intervention.
33. Presence of Hepatitis B core antibody (HbcAb) at screening or within 3 months prior to first dose of study intervention.
34. Positive Hepatitis C antibody test result at screening or within 3 months prior to first dose of study intervention.

NOTE: Subjects with positive Hepatitis C antibody due to prior resolved disease can be enrolled, only if a confirmatory negative Hepatitis C RNA test is obtained
35. Positive Hepatitis C RNA test result at screening or within 3 months prior to first dose of study intervention.

NOTE: Test is optional and subjects with negative Hepatitis C antibody test are not required to also undergo Hepatitis C RNA testing
36. Abnormal clinically significant echocardiogram at screening, as assessed by the investigator.
37. Cardiac troponin T or NT-proBNP levels out of normal range at screening.
38. Positive pre-study drug/alcohol screen.
39. Positive human immunodeficiency virus (HIV) antibody test.
40. Regular use of known drugs of abuse.
41. Estimated glomerular filtration rate (eGFR) of <90 mL/min/1.73 m² or serum creatinine >1.5xULN or urine albumin:creatinine ratio of >300mg/g at screening.

42. Positive SARS-CoV-2 PCR or rapid antigen test at screening. Participants may be rescreened once they present a negative SARS-CoV-2 PCR or rapid antigen test

Other Exclusions

43. Subjects with known COVID-19 positive contacts in the past 14 days

44. Regular alcohol consumption within 6 months prior to the study defined as:

- an average weekly intake of >21 units for males. One unit is equivalent to 8 g of alcohol: a half-pint (~240 mL) of beer, 1 glass (125 mL) of wine or 1 (25 mL) measure of spirits.

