10.2. Appendix 2: Clinical Laboratory Tests

- The tests detailed in [Table 2](#) will be performed by the local laboratory.
- Protocol-specific requirements for inclusion or exclusion of participants are detailed in Section [5](#) of the protocol.
- Additional tests may be performed at any time during the study as determined necessary by the investigator or required by local regulations.

Table 2 Protocol-Required Safety Laboratory Assessments

Laboratory Assessments	Parameters			
Haematology	Platelet Count	RBC Indices: MCV MCH %Reticulocytes	WBC count with Differential: Neutrophils Lymphocytes Monocytes Eosinophils Basophils	
	RBC Count			
	Haemoglobin			
	Haematocrit			
Clinical Chemistry ¹	Blood Urea Nitrogen (BUN)	Potassium	Aspartate Aminotransferase (AST)/ Serum Glutamic-Oxaloacetic Transaminase (SGOT)	Total and direct bilirubin (direct is only measured if total >1xULN)
	Creatinine	Sodium	Alanine Aminotransferase (ALT)/ Serum Glutamic-Pyruvic Transaminase (SGPT)	Total Protein
	Glucose (non-fasting)	Calcium	Alkaline phosphatase	³ Complement protein C3 and C4
Routine Urinalysis	
 • Specific gravity • pH, glucose, protein, blood, ketones, bilirubin, urobilinogen, nitrite, leukocyte esterase by dipstick • Microscopic examination (if blood or protein is abnormal) 			
Other Screening Tests	
 • Breath alcohol test • Urine drug screen (to include at minimum: amphetamines, barbiturates, cocaine, opiates, cannabinoids and benzodiazepines) 			

Laboratory Assessments	Parameters
	
 • HIV antibody, hepatitis B surface antigen [HBsAg], hepatitis B core antibody [HbcAb] and hepatitis C virus antibody. • QuantiFERON testUrine albumin-creatinine ratio (UACR) • ⁴SARS-CoV2 PCR or rapid antigen test 
The results of each test must be entered into the medical notes.

Other Screening and Follow-Up Tests	
 • Troponin-T (high sensitivity) • NT-proBNP

NOTES:

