5.2. Baseline Definitions

For all endpoints (except as noted in baseline definitions) the baseline value will be the latest pre-dose assessment with a non-missing value, including those from unscheduled visits. This study has three study periods, with each period having its own baseline which is the latest non-missing value prior to dosing in that period.

For the PainCart test, two assessments are performed at each visit except for visit Day 1 where two are performed prior to dose and two are performed after dose. The baseline value is defined as the mean of the two pre-dose assessments on Day 1 for each study period. If only one pre-dose assessment record is present on Day 1, then this value will be set as the baseline value.

For the PainCart analyses, baseline will compose of two variables:

- Subject level baseline = the mean of the three period baseline values for each subject.
- Period level baseline = Subject level baseline – Period specific baseline value.

Parameter	Study Assessments Considered as Baseline			Baseline Used in Data Display
	Screening	Day -1	Day 1 (Pre-Dose)	
Efficacy				
PainCart Assessments			X	Mean of Day 1 (Pre-Dose) Assessments
Safety				
Vital Signs			X	Day 1 (Pre-Dose)
Haematology			X	Day 1 (Pre-Dose)
Chemistry			X	Day 1 (Pre-Dose)
ECG			X	Day 1(Pre-Dose) [Mean of triplicate measurements]
Urinalysis			X	Day 1 (Pre-Dose)

Unless otherwise stated, if baseline data is missing no derivation will be performed and baseline will be set to missing.

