12.6. Appendix 6: Derived and Transformed Data

12.6.1. General

Multiple Measurements at One Analysis Time Point	

 Mean of the measurements will be calculated and used in any derivation of summary statistics but if listed, all data will be presented. Participants having both High and Low values for Normal Ranges at any post-baseline visit for safety parameters will be counted in both the High and Low categories of “Any visit post-baseline” row of related summary tables. This will also be applicable to relevant Potential Clinical Importance summary tables. 	
Study Period	

 The start date of Period [1/2/3] is the dosing Day 1 date for that period. The end date of Period [1/2] is the Day -1 date for the subsequent period. The end date for Period 3 and Period[1/2] if no subsequent period follows, will be the final follow up visit date, or if applicable, study withdrawal date, whichever date is earlier. 	
Study Day / Period Day	

 Study day is derived with respect to the very first dose date (Period 1): 
 Ref Date = Missing → Study Day = Missing Ref Date < Dose Date → Study Day = Ref Date – Dose Date Ref Date ≥ Dose Date → Study Day = Ref Date – (Dose Date) + 1 Period day is derived with respect to the dose date during that period: 
 Ref Date = Missing → Period Day = Missing Ref Date < Period Start Date → Period Day = Ref Date – Period Dose Start Date Ref Date ≥ Period Start Date → Period Day = Ref Date – (Period Dose Start Date) + 1 	

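### The SAP sets no potential-clinical-importance limit for troponin T or NT-proBNP, the protocol's named cardiac markers, and its baseline rules for troponin T conflict

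*SAP*

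**What the plan says.** The laboratory part of the safety endpoint (Protocol 3, SAP 2.2) is defined through values of potential clinical importance, and SAP 12.8.1 sets the laboratory limits. Its chemistry block has nine rows: albumin, calcium, creatinine, glucose, potassium, sodium, total CO2, "Creatinine kinase" (read here as creatine kinase) and "C-reactive protein". A separate block covers the liver tests. Neither block mentions troponin T or NT-proBNP.

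The protocol gives those two markers a specific job. Under cardiac risks, Protocol 2.3.1 states: "TroponinT and NT-proBNP will be monitored after dosing". Exclusion criterion 37 reads: "Cardiac troponin T or NT-proBNP levels out of normal range at screening". The in-period schedule (Protocol 1.3.2, repeated in SAP 12.2.1.2) says "Troponin T to be assessed on Day -1, 8, 15 (and EW if needed" of the early-withdrawal visit. The screening and follow-up schedule (Protocol 1.3.1) adds troponin T at screening and at final follow-up. NT-proBNP appears only at screening and final follow-up.

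On baseline, the text of SAP 5.2 takes the latest non-missing value before dosing in each period, apart from exceptions noted in that section. The table beneath it marks only Day 1 pre-dose for chemistry and leaves the Day -1 column empty. The section closes: "Unless otherwise stated, if baseline data is missing no derivation will be performed and baseline will be set to missing".

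**The concern.** Table 3.12 (worst-case chemistry against PCI criteria) and Listing 23 (laboratory data for participants with a PCI value) are the rule-based laboratory safety outputs. An analyte without a limit cannot trigger either. Here the analytes without a limit include the two markers collected for a risk the protocol names in advance, while four analytes outside the routine panel do have limits. The list does not appear to have been matched to this protocol.

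The baseline conflict adds to this. If the table in SAP 5.2 governs, scheduled troponin T has no baseline and so no change from baseline. If the text governs, it has one. Two programmers could follow the SAP faithfully and produce different tables. What is at stake is whether the study report can show, by treatment and by a rule fixed in advance, what happened to troponin T after dosing.

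**Working it through.** The plan states no figure to reproduce. The check compares lists and schedules, then counts values.

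**1. PCI list against the collected panel.** The scheduled chemistry panel (Protocol 10.2 Table 2, SAP 8.2) is BUN, creatinine, glucose, potassium, sodium, calcium, AST, ALT, alkaline phosphatase, bilirubin, total protein and C3/C4. Troponin T and NT-proBNP are listed separately as screening and follow-up tests.

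- PCI chemistry rows: 9.
- Rows outside the scheduled panel: 4 (albumin, total CO2, creatine kinase, CRP).
- Of these, required conditionally: 1. Protocol 10.5 requires CPK after a liver stopping event.
- Named nowhere as a serum test: 4 − 1 = 3.
- Collected but without a limit: troponin T, NT-proBNP, BUN, total protein, C3/C4.
- Cardiac markers with a limit: 0 of 2.

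**2. Troponin T baseline under each rule in SAP 5.2.**

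| Rule | Day allowed | Troponin T drawn then? | Result |
|---|---|---|---|
| Text: latest pre-dose value in the period | latest of the days before dosing | yes, Day -1 | baseline = Day -1 |
| Table, chemistry row | Day 1 pre-dose only | no (Days -1, 8, 15) | baseline missing, no change derived |

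**3. Which output would show a rise?**

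- Table 3.12: no, because there is no limit.
- Listing 23: not triggered. The values would appear there only if another analyte in the same participant met a limit.
- Table 3.11 (chemistry changes from baseline): needs no PCI limit, but does need a baseline and a decision to include the marker. SAP 8.2 places both markers outside clinical chemistry, whereas the schedule attaches troponin T to the chemistry row.
- Tables 3.13 to 3.16: haematology and urinalysis only.
- Listing 24 (all laboratory data): yes.
- Adverse event tables: only if the investigator judges the change clinically relevant and records it.

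**4. Number of values affected.** Scheduled post-dose troponin T per completer: 2 days × 3 periods + 1 final follow-up = 7. The Day -1 draws of Periods 2 and 3 are left out because they serve as baselines.

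- 24 completers, the protocol's target: 24 × 7 = 168.
- 30 completers, the enrolment maximum: 30 × 7 = 210.
- 15 to 18 completers: 15 × 7 = 105 to 18 × 7 = 126. This is an assumption. SAP 1.1 says the study ended after missing its futility threshold but does not give the final number.

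Each count includes draws after placebo. NT-proBNP has one scheduled post-dose value per completer.

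**The case against.** The strongest reply is that cardiac safety has other routes into the report. Protocol 8.1.4 requires the investigator to review each laboratory report and record clinically relevant changes as adverse events, which feed the tables from 3.01 onward and Listing 16. ECG values have their own limits (SAP 12.8.2) and Tables 3.17 to 3.20. An echocardiogram is repeated if clinically significant changes are seen. This stands. A reader might infer that the cardiac risk cannot appear in the safety tables at all, and the documents do not support that. These routes do not, however, supply what the PCI outputs give other analytes: a count by treatment that does not depend on individual judgement. The ECG tables do not report troponin.

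A reader might also infer that troponin T simply has no baseline. That follows only if the table in SAP 5.2 overrides its text, and if troponin T counts as chemistry. Neither is settled. The exception clause in the text makes the table reading reasonable, but what is established is a conflict.

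Nor does SAP 12.6.1 remove the Day -1 value. It says "The end date of Period [1/2] is the Day -1 date for the subsequent period", which could suggest that Day -1 of Periods 2 and 3 belongs to the preceding period. But SAP 12.3.1 reports measurements under the visit assigned in the database, and 12.6.1 itself gives dates before a period's start a period day relative to that period's dose.

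The four unmatched analytes are not all never measured, given CPK after a liver stopping event and the provision for additional tests in Protocol 10.2. Unused rows flag nothing and do no harm. A PCI list also need not cover every analyte; BUN and total protein have no limit either. The two cardiac markers differ because the protocol names them for a stated risk.

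Finally, Protocol 2.3.1 reports that the heart-weight finding was not reproduced at 26 weeks and does not regard it as clinically significant. This lowers the stakes without withdrawing the monitoring commitment.

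**Conclusion.** The point holds as a gap and a conflict in the SAP. Neither cardiac marker has a PCI limit, so a rise in either cannot trigger Table 3.12 or Listing 23. Listing 24 is the only laboratory output certain to show it. Inclusion in Table 3.11 is undefined, and the adverse event route depends on investigator judgement. The two rules in SAP 5.2 give different troponin T baselines.

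The size is seven scheduled post-dose troponin T values and one NT-proBNP value per completer, none of which can be flagged: 168 troponin T values at the planned 24 completers, and 105 to 210 over 15 to 30. These counts assume full attendance and include placebo periods. The display shells are not in the documents, so the contents of Table 3.11 could not be checked. It would go too far to say that the safety conclusion is bound to read as clean. The correction should be made before the final laboratory tables are produced, but it does not touch the primary analysis.

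**What to change.** - **SAP 12.8.1:** add troponin T (hs) and NT-proBNP with a high flag above the laboratory's normal range, the boundary exclusion 37 already uses. State that it is an analysis flag only and changes no participant management. Several existing limits sit beyond the upper limit of normal, so if the sponsor prefers another boundary it should give the reason. Align the remaining rows with the collected panel: drop albumin, total CO2 and CRP unless they are collected, and mark creatine kinase as conditional on a liver stopping event.
- **SAP 5.2:** name that period's Day -1 as the troponin T baseline, in both the text and the table.
- **SAP 8.2 and 12.11:** state that troponin T is included in Tables 3.11 and 3.12 and Listing 23.
- **NT-proBNP:** report it as a comparison of screening with final follow-up, with flagging in Listing 23. Keep it out of the by-period tables. Its only scheduled post-dose value comes after completers have received both treatments, so it cannot be attributed to one of them.

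The cost is SAP wording and a few programming lines, with no new samples or visits. The laboratory tables belong to the later reporting milestone (AAC), and the interim display lists in SAP 3.1 contain no laboratory tables. Some sponsor functions are nevertheless unblinded to interim data, so the amendment should record when the limit was set. Taking it from a boundary already in the protocol keeps the choice from being driven by the data.

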12.8.2. ECG

ECG Parameter	Units	Clinical Concern Range	
		Lower	Upper
Absolute			
Absolute QTc Interval	msec		>500
Absolute PR Interval	msec	<110	>220
Absolute QRS Interval	msec	<75	>120
Change from Baseline			
Increase from Baseline QTc	msec		>60

12.8.3. Vital Signs

Vital Sign Parameter (Absolute)	Units	Clinical Concern Range	
		Lower	Upper
Systolic Blood Pressure	mmHg	< 85	> 160
Diastolic Blood Pressure	mmHg	< 45	> 100
Heart Rate	bpm	< 40	> 110

12.9. Appendix 9: Pharmacokinetic / Pharmacodynamic Analyses

An exploratory graphical analysis of the total drug on the primary endpoints of efficacy will be performed by generating the PK/PD plots as presented in [Appendix 12](#).

If the exploratory graphical analysis suggests a relationship and data permits, a PopPK/TE model may be developed from the final PK and TE data from the first-time in human study 207804 and may be fitted to the current data using the nonlinear mixed effects modelling software NONMEM. In this case, data relative to the primary measures of efficacy will be used to model the PD effect. Direct and indirect response models may be developed from all available PD data and linked with the PK/TE to characterise the relationship between different modalities of nociception and PK or TE.

The appropriateness of the PopPK/PD model will be assessed by the OFV, successful convergence, covariance estimation, shrinkage, parameter uncertainty, standard GoF and simulation-based diagnostic plots e.g. VPC.

The GoF plots may include, but are not limited to:

- Population and individual predictions versus observations
- Conditional weighted residuals versus population predictions and time

If a VPC is performed, this will be based on 1000 simulations with the model and the design structure of the observed data (i.e. dose level and time, time of PK/PD sampling and individual values of model covariates, if any). The median and the 10th and 90th will be compared to the observed data.

If any PK/PD modelling is conducted, it will be reported in a separate CPMS modelling report, after reporting of this study.

12.9.1. Pharmacokinetic / Pharmacodynamic Dataset Specification

The dataset specification to support any PK/PD analysis will be provided as a separate document.

The merging of PK, TE, PainCart, treatment, and demographic data together with the creation of the NONMEM-specific dataset will be performed by, or under the direct auspices of, Clinical Statistics & Programming, GlaxoSmithKline.

This dataset programming will be conducted in a HARP environment using the currently supported version of SAS.

